10.1 Ocular Adverse Events

Ocular AEs that might reasonably be expected to occur include, but are not limited to, the following:

- BCVA loss of 2 lines (10 letters) or more on the ETDRS chart in comparison with the best BCVA reported in Study Protocol TMI-09-01
- Any 2-point worsening in slit lamp examination findings (other than cells and flare) to “severe or “very severe”, which is not associated with a pre-existing condition
- Chronic anterior uveitis, defined as inflammation of Grade 1+ or worse persisting for more than 3 months post-operatively or that recurs less than 3 months after discontinuation of anti-inflammatory treatment
- Endophthalmitis
- Presence of flat anterior chamber requiring anterior chamber reformation
- Presence of a shallow chamber with iridocorneal apposition without lens/cornea touch
- Corneal edema
- Corneal decompensation
- Corneal opacification
- Hyphema, which is > 2 mm in size
- Retinal detachment
- Proliferative vitreoretinopathy
- Other retinal complications (e.g., dialysis, flap tears)
- Increase in C:D ratio of ≥ 0.3 units in comparison with the 24-month C:D ratio reported in Study Protocol TMI-09-01
- A confirmed worsening in visual field mean deviation (MD) of ≥ 2.5 dB compared to the 24-month visual field MD determined in Study Protocol TMI-09-01
- Suprachoroidal hemorrhage
- Choroidal effusion requiring surgical drainage

**CYPASS® MICRO-STENT
PROTOCOL TMI-09-01-E VERSION G**

- Choroidal effusion or detachment with at least a partially hemorrhagic component that obstructs vision or causes pain (including both peripheral and “kissing” choroidal detachments) lasting longer than 30 days
- Hypotonic maculopathy
- Macular edema (including cystoid macular edema and diabetic macular edema)
- Choroidal folds
- Other maculopathy
- Clinically significant hypotony, which is defined as IOP < 6 mmHg that results in maculopathy; flat anterior chamber requiring reformation; corneal folds; onset or worsening of with-the-rule astigmatism by ≥ 1 Diopter or rotation of against-the-rule to with-the-rule astigmatism by ≥ 1 Diopter; choroidal effusion requiring surgical drainage; suprachoroidal hemorrhage or BCVA loss of ≥ 2 lines
- Mean (or median) IOP ≥ 10 mmHg higher than the subject’s baseline mean unmedicated diurnal IOP reported in Protocol TMI-09-01
- CyPass device obstruction by iris, vitreous, lens, fibrous overgrowth, fibrin or blood
- CyPass device malfunction
- CyPass device malposition or dislodgement, defined as CyPass positioning after deployment such that:
 - The device is not in the supraciliary space, or
 - There is a clinical sequela resulting from device position including, but not limited to:
 - Secondary surgical intervention to modify device position (e.g., repositioning, proximal end trimming or explantation)
 - Corneal endothelial touch by device
 - Corneal edema leading to loss of BCVA > 2 lines at the last postoperative visit in comparison with preoperative BCVA
 - Progressive ECL, defined as reduction in endothelial cell count of 30% or more relative to baseline ECD value
 - Erosion of device through sclera
 - Device obstruction requiring secondary surgical intervention.
- CyPass device exposure or extrusion
- Other events that necessitate unplanned intraocular surgical re-intervention (other than Nd:YAG capsulotomy), which includes, but is not limited to CyPass explantation, CyPass repositioning, CyPass trimming, planned CyPass lumen occlusion and treatment of elevated IOP that is not satisfactorily managed using ocular hypotensive medication
- Significant ptosis
- Atrophy/phthisis
- Wound dehiscence, which is defined as persistent aqueous leak or fistula formation
- Vitreous hemorrhage
- Chronic ocular pain, which is defined as continuous pain documented at 2 visits at least 30 days apart not associated with a pre-existing condition
- Significant foreign body sensation

**CYPASS® MICRO-STENT
PROTOCOL TMI-09-01-E VERSION G**

- Any 2-point worsening of an ocular symptom questionnaire report to “severe” or “very severe”, which is not associated with a pre-existing condition

10.2 Sight-Threatening Ocular Adverse Events

Sight-threatening AEs include, but are not limited to endophthalmitis, corneal decompensation, BCVA loss ≥ 3 lines, severe retinal detachment, severe choroidal hemorrhage, severe choroidal detachment and aqueous misdirection.

10.3 Grading of Adverse Events

Adverse events will be categorized by degree of harm to the subject using the 3-point scale below:

- Mild: Discomfort noticed, but there is no disruption of normal daily activity
- Moderate: Discomfort is sufficient to reduce or affect normal daily activity
- Severe: Incapacitation as evidenced by the inability to work or perform normal daily activity

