5.1 Study Outcomes

5.1.1 Primary Outcome – Safety

- Rate of occurrence of sight-threatening AEs

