8.3 Unscheduled Visits

Unscheduled visits are clinic visits not specified in the protocol when the subject returns for examination due to a complaint regarding the study eye or a surgical procedure performed on the study eye. No specific testing is required at unscheduled visits; rather, the investigator and/or qualified investigational staff will perform the examinations or procedures necessary to evaluate the subject at these visits. Clinical data from unscheduled visits will be recorded on the relevant eCRF.

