10 ADVERSE EVENTS

All ocular AEs occurring in the study eye must be reported on the relevant eCRF. Adverse events will be categorized by degree of harm to the subject (mild, moderate, or severe) and the relationship to the CyPass Micro-Stent. Since there are no aspects of the study that can affect both eyes, only serious adverse events observed in the fellow eye must be reported. Serious non-ocular AEs will also be captured on the relevant eCRF throughout the course of the study.

Ocular conditions or diseases present at the time of study enrollment in Study Protocol TMI-09-01 will be considered as “baseline”. Changes in a chronic condition or disease that are consistent with natural disease progression are not considered to be AEs. The status of AEs that were “ongoing” at subject exit from Study Protocol TMI-09-01 will be evaluated at the time of enrollment in this study. Events that remain ongoing and that meet the AE definitions for this protocol will be documented as AEs in this study

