5.1 Sight Threatening Ocular Adverse Events

Sight-threatening AEs include, but are not limited to, BCVA loss of ≥ 3 lines, endophthalmitis, corneal decompensation, severe retinal detachment, severe choroidal hemorrhage, severe choroidal detachment and aqueous misdirection. A non-parametric time to event Kaplan-Meier (K-M) analysis for the sight-threatening AE rate at 5 years will be performed, stratified by treatment group. This method accounts for all information that discontinued subjects contribute

to the rate of the primary safety event up to the point at which that subject discontinues (i.e., is censored). The cumulative Kaplan-Meier probability and associated and 95% confidence intervals that a subject experienced a sight-threatening AE will be provided for each treatment group at 5 years.

To aid in the interpretation of the results, the annualized rates (percentages) for each year and over the 5-year period will also be calculated using the LIFETEST procedure. There will be no covariate adjustments in the model as the only factor will be treatment group.

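### Three primary-outcome components must be *severe* to meet their named definition, and the only definition of *severe* is general incapacitation, so sight-threatening study-eye events can be missed or counted unevenly

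*Protocol*

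**What the plan says.** The primary outcome (Protocol 5.1.1) is "Rate of occurrence of sight-threatening AEs". Protocol 9.1, Protocol 10.2 and SAP 5.1 name the same seven events. Four are unqualified: BCVA loss of 3 lines or more, endophthalmitis, corneal decompensation and aqueous misdirection. The other three are qualified, as the end of the SAP 5.1 list shows: "severe retinal detachment, severe choroidal hemorrhage, severe choroidal detachment and aqueous misdirection". The list is illustrative; Protocol 10.2 opens with "Sight-threatening AEs include, but are not limited to endophthalmitis, corneal decompensation".

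Protocol 10.3, the section directly after 10.2, states: "Adverse events will be categorized by degree of harm to the subject using the 3-point scale below". The top grade reads "Severe: Incapacitation as evidenced by the inability to work or perform normal daily activity". The two lower grades are defined by discomfort and its effect on daily activity. No grade mentions vision or the eye, and the SAP adds no definition.

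SAP 5.1 analyses the outcome by Kaplan-Meier at 5 years for each treatment group, and SAP section 4 says that no hypotheses are tested.

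**The concern.** Each subject contributes one study eye. Someone with a useful fellow eye can have a retinal detachment or choroidal hemorrhage that threatens sight in the study eye and still work and live normally. Under 10.3 that event is mild or moderate, so it does not meet the named component.

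The study exists to describe long-term safety and has no test or decision threshold, so the estimated primary rates are its main result. Two of the three qualified components are choroidal, and Protocol 4.1 says the device drains into the supraciliary and suprachoroidal spaces. These are events on which the primary rate should be dependable. Investigators can also know the treatment group: gonioscopy is done only in CyPass eyes (Protocol 8.2, Appendix 1), and they classify each event's relationship to the device (Protocol 10). A loosely defined inclusion decision is therefore not protected by masking.

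**Working it through.** The plan gives no expected event rate, arm size or power figure for this outcome, so there is no figure to reproduce. The check is a comparison of sections, followed by an illustration of size.

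**Step 1: what *severe* can mean.**
- If it is the 10.3 grade, entry for three of the seven named components depends on whole-person incapacitation.
- If it is an ordinary adjective, those components have no criterion and no named decision-maker. Protocol 10.1 shows that the plan can write eye-specific criteria: it gives a size limit for hyphema, and for choroidal effusion a need for drainage or a minimum duration.

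Either reading leaves the numerator poorly defined. The first gives the wrong one.

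**Step 2: trace one event.** Take a study-eye retinal detachment in a subject who is not incapacitated.

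| Route into the primary outcome | Result |
|---|---|
| Named component, with the 10.3 grade | Not met |
| BCVA loss of 3 lines or more | Met only if a loss of that size is measured |
| Open-ended list | Possible, but no rule, adjudication or masking is stated |

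On the second route, scheduled BCVA is yearly (36, 48 and 60 months). Between those visits Protocol 8.3 says "No specific testing is required at unscheduled visits". Smaller losses, and losses that are treated or recover before a test, can go unrecorded. The exposed events are those that take neither the first nor the second route.

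**Step 3: size, for illustration.** One omitted event lowers a crude arm proportion by 100/n percentage points. Arm sizes are not in the documents; 120, 240 and 360 are assumed, and 480 is the stated maximum for the whole study.

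| n | 100/n (points) |
|---|---|
| 120 | 0.83 |
| 240 | 0.42 |
| 360 | 0.28 |
| 480 | 0.21 |

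Two examples with assumed event counts and exact Clopper-Pearson 95% intervals, ignoring censoring:
- n = 360, 8 true events: 8/360 = 2.22% (0.96 to 4.33). With 2 omitted: 6/360 = 1.67% (0.61 to 3.59).
- n = 120, 4 true events: 4/120 = 3.33% (0.92 to 8.31). With 2 omitted: 2/120 = 1.67% (0.20 to 5.89), half the rate.

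The intervals overlap widely. The examples show how sensitive a rare-event rate is to a few inclusion decisions; they do not predict a bias.

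**The case against.** The strongest reply is that the text excludes nothing. The list is open, and neither Protocol 10.2 nor SAP 5.1 cites the 10.3 grade. *Severe* is also used on other scales (slit lamp findings and the symptom questionnaire in 10.1), so it is not reserved for 10.3. Appendix 2 is not visible and might hold a definition. This stands to the extent that the link to 10.3 is an inference. It does not remove the problem: 10.3 covers all adverse events and is the only definition available, while Protocol 8.2 describes Appendix 2 as examination methodology. An open list with no entry rule replaces exclusion with discretion.

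Second, BCVA loss of 3 lines or more counts whatever its cause, and unscheduled visits include whatever examinations the investigator judges necessary. This stands in large part: it recovers many events and narrows the gap to those with smaller, unmeasured or recovered loss. Omitting minor cases may even be the purpose of the qualifier, but incapacitation is a poor way to identify them.

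Third, the events are not lost from the report. Protocol 10.1 lists retinal detachment and suprachoroidal hemorrhage without a severity condition, and SAP 5.2 tabulates protocol-specified and other ocular events with exact intervals and listings. This stands for the secondary tables. Those tables do not restore the events to the Kaplan-Meier composite.

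A reader might go further and infer that these events count only when incapacitating, that the undercount has a known size, or that it favours one arm. The documents support none of these. The open list defeats the first. On the second, if true risk were 5%, one third of it came from these components and 10 to 50% of those were graded severe, the reported risk would be 3.33% + (0.10 to 0.50) × 1.67% = 3.5 to 4.2%, a relative loss of 17 to 30%. All three inputs are assumed and BCVA recovery is ignored, so the result only restates the inputs. On the third, no section suggests that grading differs by arm.

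**Conclusion.** The point holds as a defect in the definition of the primary outcome. Applying the protocol's own meaning of *severe* gives a numerator that can omit sight-threatening study-eye events; declining to apply it leaves three components without a criterion. Either way the rate can be too low or can vary between sites.

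The magnitude is not derivable from the documents. All that can be said is about 0.3 to 0.8 percentage points of crude arm rate per omitted event, for assumed arms of 360 to 120 subjects. A difference between arms is possible, given the device's drainage route and the lack of masking, but it is not shown. The conclusion assumes that no definition of *severe* sits in text that could not be seen.

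**What to change.** 1. In Protocol 10.2 and SAP 5.1, and in Protocol 9.1 which repeats the list, state that the 10.3 severity grade does not decide entry to the primary outcome.
2. For retinal detachment, choroidal hemorrhage and choroidal detachment, replace *severe* with an eye-specific criterion based on data already collected, for example that the event led to intraocular surgery. Do not rest it on the Protocol 10.5 seriousness criterion alone: that criterion names sight-threatening events but explains itself by disruption of ordinary life, so it brings back the same whole-person test.
3. Add to SAP 5.1 a Kaplan-Meier sensitivity analysis of the composite, by treatment group, counting every study-eye retinal detachment, choroidal hemorrhage and choroidal detachment regardless of grade.

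The cost is wording and programming, since all study-eye ocular adverse events are already reported. The reported rate may be slightly less favourable, and the all-grade analysis will include some minor events. Because enrollment began in April 2016, this clarifies a primary outcome in a running study and should be dated and reported as such.

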10.4 Follow-up of Adverse Events

Adverse events will be followed until resolution or stabilization of the event.

10.5 Expedited Reporting of Adverse Events

Serious adverse events (SAE) require expedited reporting to the sponsor or designee regardless of relationship to the CyPass Micro-Stent. An AE is classified as SERIOUS if it:

- Caused or led to death
- Was life-threatening (i.e., the AE placed the subject at immediate risk of death)
- Required or prolonged inpatient hospitalization (i.e., the AE required at least a 24-hour inpatient hospitalization or prolonged a hospitalization beyond the expected length of stay)
- Was sight-threatening, or otherwise disabling (i.e., the AE resulted in a substantial disruption of the subject's ability to carry out normal life functions)
- Resulted in a congenital anomaly/birth defect (i.e., an adverse outcome in a child or fetus of a subject due to participation in this study)
- Does not meet any of the above serious criteria but jeopardized the subject by requiring medical or surgical intervention to prevent one of the outcomes listed above.

All SAEs must be reported immediately (within 24 hours) of the Investigator’s or site’s awareness.

An unanticipated adverse device effect (UADE) is any serious adverse effect on health or safety, any life-threatening problem or death caused by, or associated with the CyPass Micro-Stent, that has not been previously identified. UADEs must be reported within 24 hours of the Investigator’s or site’s awareness.

**CYPASS® MICRO-STENT
PROTOCOL TMI-09-01-E VERSION G**

Adverse device effects (ADE) and/or device malfunctions that do not meet seriousness criteria and/or are anticipated must be reported within 10 calendar days of the Investigator's or site's awareness.

If product is returned in relation to an AE, a printed copy of the completed relevant AE eCRF must be included with the product return.

Reports should be submitted via the sponsor's electronic data capture (EDC) system. Document all relevant information such as concomitant medications, Discharge summary, Autopsy report, Certificate of Death etc. associated with the AE as part of the subject narrative, if applicable. Should the EDC system become non-operational, complete a paper copy of the relevant eCRF and fax to the sponsor at [REDACTED] in accordance with the timelines stated above. Once the EDC system becomes operational; enter the reported information into the EDC system. Additional relevant information after initial reporting must be entered into the eCRF promptly after the data become available.

11 STUDY MONITORING

Study monitoring will be performed in accordance with the sponsor's clinical standard operating procedures (CSOP). A combination of central and on-site monitoring activities will be utilized to confirm study site adherence to the study protocol and associated regulatory requirements, as well as to confirm appropriate reporting of study AEs. Observations from on-site monitoring visits and resulting action items will be documented and maintained in the study master file.

12 ETHICAL AND REGULATORY CONSIDERATIONS

This protocol was designed, and will be conducted in accordance with the recommendations guiding physicians in biomedical research involving human subjects adopted by the 18th World Medical Assembly, Helsinki, Finland, 1964 and later amendments. Basic responsibilities of the study sponsor, investigators and overseeing Institutional Review Board(s) (IRB) are as noted below:

12.1 Sponsor Responsibilities

The sponsor is responsible for maintaining clinical study records and reports as noted below for at least 2 years following study termination or completion. The Sponsor will make these records available for audit and review by FDA as requested by the Agency.

Clinical Study Records:

- AEs and UADEs
- Signed Investigator Agreements and Investigator *Curriculum Vitae* (CV)
- Financial disclosure information under 21 CFR Part 54
- Study eCRFs

**CYPASS® MICRO-STENT
PROTOCOL TMI-09-01-E VERSION G**

- Study-related correspondence

Clinical Study Reports:

- Written evaluation of any UADEs will be provided to all Investigators, IRBs and FDA within 10 working days of receipt of notice of the event
- Written notice of withdrawal of IRB approval will be provided to all Investigators, IRBs and FDA within 5 working days
- Annual study progress reports to all IRBs (if required by the IRB, progress reports will be submitted at greater frequency than annual)
- Annual progress reports to FDA
- Final report to all IRBs and FDA within 6 months of study termination or completion

12.2 Investigator Responsibilities

Each principal investigator is required to sign an Investigator Agreement, which documents the investigator's obligations with respect to protocol adherence, subject informed consent, and safety event reporting. By signing the Investigator Agreement, the investigator acknowledges his/her commitment to the sponsor that he/she will comply with the protocol and study obligations. All investigators must participate in a protocol review conducted by the sponsor or designated representative. No changes in this protocol can be made without the written approval of the sponsor and the overseeing IRB(s).

The investigator is responsible for the subject informed consent process and for confirming that all subjects provide written informed consent prior to enrollment in the study and that those subjects enrolled conform to study protocol eligibility criteria.

The investigator is responsible for maintaining clinical study records and reports as noted below for at least 2 years following study termination or completion. The Investigator will make these records available for audit and review by the Sponsor, IRB and/or FDA as requested.

Clinical Study Records:

- Study protocol and any amendments
- Subject source documents (e.g., medical records) including case history, documentation that informed consent was obtained prior to study participation, and description of circumstances if informed consent was not obtained
- Subject eCRFs
- Signed and dated ICDs for each subject
- Study-related correspondence

Clinical Study Reports:

- Continuing review reports to IRB and Sponsor, at least annually or as required by IRB
- Any other records required by the IRB

**CYPASS® MICRO-STENT
PROTOCOL TMI-09-01-E VERSION G**

12.3 Institutional Review Board Responsibilities

This protocol and the subject ICD must be reviewed and approved by an IRB operating in accordance with local procedures and 21 CFR Parts 50, 56, and 812 before enrollment of subjects. The Investigator is responsible for maintaining IRB approval for the study protocol and ICD and for keeping the IRB informed of protocol amendments and AEs in accordance with IRB requirements.

[figure not shown]
**CYPASS® SYSTEM 241-S
PROTOCOL TMI-09-01-E VERSION G**

**APPENDIX 1
SCHEDULE OF EVENTS AND PROCEDURES**

[figure not shown]
PROCEDURE/EXAMINATION ¹	36 MO 1095 ± 90 DAYS POSTOPERATIVE	48 MO 1460 ± 90 DAYS POSTOPERATIVE	60 MO 1825 ± 90 DAYS POSTOPERATIVE
Informed Consent	X		
Medical History Update	X	X	X
Ocular Hypotensive Medications	X	X	X
Manifest Refraction	X	X	X
BCVA (ETDRS), based on Total Letters Read	X	X	X
IOP (using Goldmann Tonometry)	X	X	X
Slit Lamp Biomicroscopy	X	X	X
Gonioscopy (only for subjects in the CyPass group)	X	X	X
Dilated Fundus Exam, including Cup to Disc (C:D) Ratio	X	X	X
Central Corneal Thickness (using Pachymetry)	X	X	X
Specular Microscopy (ECD)	X	X	X
AE Assessment	X	X	X
Visual Field (Humphrey 24-2 SITA Standard)	X	X	X
Subject Symptom Questionnaire	X	X	X

¹ All ophthalmic procedures/examinations will be performed on the study eye only

[figure not shown]
CYPASS® SYSTEM 241-S
PROTOCOL TMI-09-01-E VERSION G

[figure not shown]
**CYPASS® MICRO-STENT
PROTOCOL TMI-09-01-E VERSION G**

[figure not shown]
**CYPASS® MICRO-STENT
PROTOCOL TMI-09-01-E VERSION G**

[figure not shown]
**CYPASS® MICRO-STENT
PROTOCOL TMI-09-01-E VERSION G**

[figure not shown]
**CYPASS® MICRO-STENT
PROTOCOL TMI-09-01-E VERSION G**

[figure not shown]
**CYPASS® MICRO-STENT
PROTOCOL TMI-09-01-E VERSION G**

[figure not shown]
**CYPASS® MICRO-STENT
PROTOCOL TMI-09-01-E VERSION G**

[figure not shown]
**CYPASS® MICRO-STENT
PROTOCOL TMI-09-01-E VERSION G**

[figure not shown]
**CYPASS® MICRO-STENT
PROTOCOL TMI-09-01-E VERSION G**

**CYPASS® MICRO-STENT
PROTOCOL TMI-09-01-E VERSION G**

[figure not shown]
**CYPASS® MICRO-STENT
PROTOCOL TMI-09-01-E VERSION G**

[figure not shown]
CYPASS® MICRO-STENT
PROTOCOL TMI-09-01-E VERSION G

[figure not shown]
**CYPASS® MICRO-STENT
PROTOCOL TMI-09-01-E VERSION G**

**CYPASS® MICRO-STENT
PROTOCOL TMI-09-01-E VERSION G**

[figure not shown]
**CYPASS® MICRO-STENT
PROTOCOL TMI-09-01-E VERSION G**

**CYPASS® MICRO-STENT
PROTOCOL TMI-09-01-E VERSION G**

**CYPASS® MICRO-STENT
